## **ANALYSES OF THE SECONDARY EFFICACY CRITERIA**

All analyses of the secondary efficacy criteria will be performed on the ITT data set (*defined in section 7.B.3.1*).

**The number of hospital days due to severe COPD exacerbations** will be analysed in exactly the same way as the primary efficacy criterion, including its primary, supportive and additional analyses previously described.

**The number of moderate and severe COPD exacerbations** separately as recorded by the investigators will be compared between both study groups with the Wilcoxon's rank sum test, in all countries pooled together.

**Time to first severe COPD exacerbation** (*expressed in number of days*) throughout the *Follow-Up Period* will be tabulated by study group, as quantitative data, in the subgroup of patients from the ITT data set experiencing at least one severe COPD exacerbation during their *Follow-Up Period*, as reported by the investigators, in all countries pooled together. Moreover, time to first severe COPD exacerbation throughout the *Follow-Up Period* will be described globally by study group, on the ITT data set, using Kaplan-Meier's estimates to display the probability of survival and of experiencing severe COPD exacerbation. Survival times will be censored at the earliest time of occurrence of the following events:

- the patients' last contact (*this will apply to the subgroup of patients who never experience any severe COPD exacerbation and who are never hospitalised for any reason during their Follow-Up Period*),
- the time to first severe COPD exacerbation (*for the subgroup of patients experiencing at least one severe COPD exacerbation during their Follow-Up Period*),
- the time to first hospital admission for another reason than COPD exacerbation (*for the subgroup of patients hospitalised at least once during their Follow-Up Period*),
- the time to death for another reason than COPD exacerbation, if applicable.

If relevant, time to first severe COPD exacerbation will be compared between both study groups with the Log rank test.

**The use of health care services due to COPD and to all causes** separately will be tabulated by study group and type or unit of time (*i.e., qualitatively in terms of volume without being priced*). Each category separately will be compared between both study groups using either the Student's t test or the Wilcoxon's rank sum test depending on their distribution.

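### The censoring rule for time to first severe COPD exacerbation lists the event itself as a censoring time and also censors at the first non-COPD admission, so it discards observed events and needs rewriting

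*Protocol*

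**What the plan says.** Section 7.B.3.5, under the analyses of the secondary efficacy criteria, handles time to first severe COPD exacerbation in two ways.

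- A quantitative table by group covers every ITT patient with at least one severe exacerbation in the Follow-Up Period.
- A time-to-event analysis covers the whole ITT set, "using Kaplan-Meier's estimates to display the probability of survival and of experiencing severe COPD exacerbation". For this analysis, "Survival times will be censored at the earliest time of occurrence of the following events":
  1. last contact, for patients "who never experience any severe COPD exacerbation and who are never hospitalised for any reason";
  2. "the time to first severe COPD exacerbation";
  3. "the time to first hospital admission for another reason than COPD exacerbation";
  4. "the time to death for another reason than COPD exacerbation, if applicable".

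The comparison is conditional: "If relevant, time to first severe COPD exacerbation will be compared between both study groups with the Log rank test".

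Section 6.A.2.2 defines a severe exacerbation as one that leads to hospital admission or death, and dates it by the admission or the death. It makes no exception for a patient who was admitted earlier for something else. Section 7.B declares everything apart from the primary analysis exploratory and descriptive.

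**The concern.** Two of the four items do not belong in a list of censoring times.

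Item 2 is the event whose timing is being estimated. No outcome is named in the paragraph that is not also a censoring time, so the rule defeats the stated purpose of the curve.

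Item 3 removes a patient from the risk set at an admission that does not end observation. A non-COPD admission is not a reason for withdrawal in section 3.D, and exacerbations continue to be recorded at each later visit (section 4.B.3.2). The item is not limited to unscheduled admissions, so a planned admission would also end a patient's contribution. A severe exacerbation after any of these is in the database but is dropped from the curve and the test.

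At stake is the time-to-event display of the outcome that section 1.C expects the programme to reduce. The number of events, the question that the log-rank test answers, and possibly the level of the curve all depend on this rule.

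**Working it through.** **Plan's own figures.** The protocol gives no event count, admission rate, hazard ratio or power for this endpoint, so there is nothing of its own to reproduce. Two inputs come from section 7.B.2: 153 patients per group (143/(1 − 0.0625) = 152.5, rounded up, as stated) and dropout of 25% per year. All admission rates below are assumptions.

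**Step 1: the literal rule.** If every item is a censoring time, all 306 patients are censored. There are 0 events, Kaplan-Meier stays at 100% event-free, the log-rank variance is 0 and the statistic is undefined.

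**Step 2: the charitable rule.** Take item 2 as the event and keep item 3. Consider a patient with a non-COPD admission at month 3 and a first severe exacerbation at month 7:

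- quantitative table: counted, with a time of 7 months;
- Kaplan-Meier and log-rank: censored at month 3, event not counted.

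Two displays of one endpoint in the same paragraph therefore report different numbers of events.

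**Step 3: size in closed form, with correlated admissions.** Assume 0.9 severe exacerbations per year, r non-COPD admissions per year, and a patient-level gamma frailty (mean 1, variance 1) that multiplies both rates. There is no dropout in this step.

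- True 12-month risk: 1 − 1/(1 + 0.9) = 47.4%.
- Share of first exacerbations within 12 months that follow a non-COPD admission: r/(1.9 + r).
- What Kaplan-Meier estimates with item 3 in force: 1 − (1.9 + r)^(−0.9/(0.9 + r)).

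| r per year | Events discarded | Kaplan-Meier risk at 12 months |
|---|---|---|
| 0.2 | 0.2/2.1 = 9.5% | 45.5% |
| 0.4 | 0.4/2.3 = 17% | 43.8% |
| 0.6 | 0.6/2.5 = 24% | 42.3% |

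The displayed risk is too low by 1.9, 3.6 and 5.1 points.

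**Step 4: simulation at the trial's size.** Settings: 153 per group, 365 days, 25% yearly dropout, hazard ratio 0.65 for severe exacerbation, and non-COPD admissions equally frequent in both groups. The control 12-month risk of severe exacerbation is 40% or 60%, and the risk of non-COPD admission is 10% to 40% (at average frailty where frailty applies). There were 1,000 trials per setting. Each cell shows item 3 removed → item 3 kept; the two ends of the non-COPD range are shown.

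| Exacerbation risk | Non-COPD risk | Admissions | Events | Power | Control 12-month risk |
|---|---|---|---|---|---|
| 40% | 10% | independent | 91.6 → 87.5 | 54.3% → 52.2% | 40.0% → 40.0% |
| 40% | 40% | independent | 91.7 → 73.9 | 54.9% → 47.5% | 40.1% → 40.1% |
| 60% | 10% | independent | 141.6 → 135.6 | 71.3% → 68.7% | 59.7% → 59.7% |
| 60% | 40% | independent | 141.7 → 116.0 | 71.9% → 64.0% | 59.9% → 59.9% |
| 40% | 10% | shared frailty | 79.5 → 74.4 | 36.4% → 36.1% | 33.9% → 32.9% |
| 40% | 40% | shared frailty | 79.5 → 59.4 | 36.5% → 29.8% | 33.7% → 29.5% |
| 60% | 10% | shared frailty | 116.0 → 109.7 | 46.1% → 45.2% | 47.6% → 46.6% |
| 60% | 40% | shared frailty | 116.3 → 91.2 | 44.1% → 38.3% | 47.9% → 43.3% |

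With independent admissions, about 4% to 19% of events are lost, power falls by about 2 to 8 points, and the curve is unbiased. With a shared frailty, about 5% to 25% of events are lost, power falls by about 0 to 7 points, and the control risk is too low by about 1 to 5 points.

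**The case against.** The best defence of item 2 is that it is a wording slip. The bullets can be read as the times at which observation ends, and both the purpose of the curve and the log-rank sentence show that the exacerbation is meant to be the event. A zero-event analysis would also be noticed at once. That is probably right, and it makes item 2 a drafting error rather than a source of bias. It does not help item 3.

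The defence of item 3 is that its effect is modest and depends on assumptions. The bias comes entirely from the assumed correlation, and with independent admissions the curve is not shifted. This stands as a limit on size. Section 1.A, which links comorbidities to multiple hospitalisations, makes a positive correlation plausible but does not establish it.

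A reader might infer more than the protocol supports, in four ways.

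- *That the log-rank test is invalid.* It is not. With item 3 in force it is a legitimate test of a different quantity.
- *That the two groups are distorted differently.* The programme could change non-COPD admissions, but nothing in the protocol shows this, and the calculation gives both groups the same non-COPD rate.
- *That censoring other-cause deaths* ("the time to death for another reason than COPD exacerbation") *is wrong for the test.* A cause-specific log-rank test does exactly that. Only reading one minus Kaplan-Meier as an absolute probability is affected, and that effect is not quantified here.
- *That the trial's conclusion is at risk.* The primary Wilcoxon test, the comparison of exacerbation counts and the quantitative table do not use this rule.

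**Conclusion.** Wrong as written; should be fixed. The rule names its own event as a censoring time, which read literally leaves nothing to analyse. It also censors at non-COPD admission, which departs from the endpoint in section 6.A.2.2 and disagrees with the table in the same paragraph. These points rest on the text alone.

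The size rests on assumptions: about 4% to 25% of first severe exacerbations lost for 12-month non-COPD admission risks of 10% to 40%, with a power loss of up to about 8 points. A downward shift of about 1 to 5 points in the displayed 12-month risk appears only if the two kinds of admission are positively correlated. The analysis is secondary, exploratory and tested only if judged relevant, so this is not a threat to the primary result.

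**What to change.** Rewrite the bullet list in section 7.B.3.5 before database lock:

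- **Event:** first severe COPD exacerbation, dated by hospital admission or by death from COPD exacerbation.
- **Non-COPD admission:** delete it as a censoring time; these patients stay at risk.
- **Censoring:** every event-free patient, whether or not hospitalised, is censored at last contact or at the end of his or her own Follow-Up Period. The last-contact item now covers only patients never hospitalised, so it must be widened. Do not truncate everyone at 12 months: sections 7.B.3.5 and 7.B.3.7 refer to first-enrolled patients followed to Month 24, and truncation would again drop observed events.
- **Other-cause death:** keep it censored for the log-rank test and call that test cause-specific. Show the probability of exacerbation as a cumulative incidence curve with other-cause death as a competing event.

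The cost is one rewritten list and one extra standard curve. The admission dates, reasons for admission and death dates are already collected, so no new data are needed.

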## 5.D CONCOMITANT TREATMENTS

All concomitant treatments administered to the patient (*including vaccines, oxygen therapy, home ventilation and CPAP*) will be recorded by the investigators in the e-CRF, with the following information:

- **For the pharmaceutical therapies:** treatment names and dosage, route of administration, dose per administration and posology, start and end dates or ongoing medication, and the reason for their prescription,
- **For the vaccines:** names and date of administration,
- **For oxygen therapy:** start and, if applicable, end dates, daily prescribed hours of use, prescribed flow rates (*at rest, during exercise and during sleep*), type of oxygen source(s) including the name of the device(s) used,
- **For home ventilation and CPAP:** start and end dates, if applicable.

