In the subgroup of patients on oxygen therapy at Selection and/or during their study participation and on the period of their oxygen prescription overlapping their holding of the *NOWOX* device, the average daily duration prescribed will be tabulated by study group. For each patient for whom a change in the daily duration of oxygen prescription is recorded throughout the *Follow-Up Period*, the individual daily duration of oxygen prescription will be estimated by using the sum of all recorded daily durations prescribed multiplied by the number of days of the corresponding prescription, divided by the total number of days on oxygen therapy. In case of missing or incomplete information necessitating monthly approximation in this average calculation, it will be considered that each month lasts 30.5 days.

**Compliance to oxygen therapy:** in the subgroup of patients on oxygen therapy at Selection and/or during their study participation and on the period of their oxygen prescription overlapping their holding of the *NOWOX* device, the average daily use of oxygen therapy over 24 hours, as well as the average use of oxygen therapy at night (*i.e., over the time interval [22:00 ; 6:00]*) and the average use of oxygen therapy during the day (*i.e., over the time interval [06:00 ; 22:00]*) will be calculated separately over at most eight (8) successive periods (*for the first patients included in the study who have been followed up 24 months*) defined by the scheduled visits of the patients at the investigational centre, without taking into account the recordings collected by the *NOWOX* device on the day of each actual visit, *i.e.,* when applicable, over the successive periods:

- between the day following the actual date of Visit 1 and the day preceding the actual date of Visit 2 (*both included*) (*period 1*),
- between the day following the actual date of Visit 2 and the day preceding the actual date of Visit 3 (*both included*) (*period 2*),
- ... and so on, up to the last period between the day following the actual date of Visit 8 and the day preceding the actual date of Visit 9 (*both included*) (*period 8, if applicable*).

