Additionally, for each unscheduled hospitalisation separately, the average daily use of oxygen therapy and its two (2) components separately will be calculated separately over the week (*i.e., the 7 days*) preceding each unscheduled hospital admission and over the week (*i.e., the 7 days*) following each unscheduled hospital discharge, without taking into account the recordings collected by the *NOWOX* device on the days of hospital admission and discharge. These weekly means will be tabulated by study group and sequential number of hospitalisation, over each 7-day period separately, using quantitative descriptive statistics. No statistical test will be performed.

In the subgroup of patients on oxygen therapy at Selection and/or during their study participation and on the period of their oxygen prescription overlapping their holding of the *NOWOX* device, for each patient and each day on oxygen prescription, the relative difference ‘ $100 \times (\text{daily use of oxygen therapy over 24 hours as estimated by the } NOWOX \text{ device} - \text{corresponding individual daily duration of oxygen prescription } (D_{O2 \text{ prescribed}})) / D_{O2 \text{ prescribed}}$ ’ will be calculated, as well as the absolute difference ‘ $\text{daily use of oxygen therapy over 24 hours as estimated by the } NOWOX \text{ device} - \text{corresponding individual daily duration of oxygen prescription } (D_{O2 \text{ prescribed}})$ ’.

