Both differences will be tabulated by study group, over the successive periods between the scheduled visits of the patient at the investigational centre previously defined, separately and globally, using quantitative descriptive statistics. These tabulations, as well as their graphical representations and analyses over time described below will be performed twice in the subgroup of patients on oxygen therapy at any time throughout their study participation and on the period of their oxygen prescription overlapping their holding of the *NOWOX* device: first, on all recordings collected by the *NOWOX* device for all patients constituting the ITT data set, and second, on the recordings collected on the days when patients from the ITT data set are not on any concomitant respiratory assistance (*i.e., Continuous Positive Airway Pressure (CPAP) therapy and/or home Non-Invasive Ventilation (NIV)*) as reported by the investigators. They will be repeated in a second step in the subgroup of patients on continuous LTOT (*i.e., with daily oxygen duration prescribed of 15 hours or more*) at any time throughout their study participation and on the period of their LTOT prescription overlapping their holding of the *NOWOX* device.

Arithmetic means of both average differences separately and their 95.0% confidence intervals will be represented graphically (*the x-axis being the period-axis and the y-axis being the arithmetic mean-axis*) with both study groups being represented separately on the same graph. Moreover, in each study group separately, individual average relative differences will be plotted by corresponding individual daily duration of oxygen prescribed. The same graph will be produced for individual average absolute differences. If a linear or a quadratic trend can be foreseen in any study group, appropriate regression models may be evaluated to assess statistically the trend observed.

Moreover, for each average difference, separate global parametric analyses of variance on repeated measurements will be performed using the same model as the one previously described for the average daily use of oxygen therapy.

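### Protocol 7.B.3.5: daily oxygen use is compared with a prescribed duration whose only definition, when the prescription changes, is a whole-period average, so a fully compliant patient can show false under- or over-use by period

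*Protocol*

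**What the plan says.** All the relevant text is in Protocol 7.B.3.5, under the analyses of the secondary efficacy criteria.

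- **Prescription of oxygen therapy.** The averaging rule applies to any patient with a recorded change in prescribed daily hours during follow-up. For such a patient "the individual daily duration of oxygen prescription will be estimated by using the sum of all recorded daily durations prescribed". Each prescribed duration is weighted by the days it applied, and the total is divided by all days on oxygen. The result is one time-weighted mean per patient.
- **Compliance to oxygen therapy.** A relative and an absolute difference between NOWOX-recorded use and prescription are calculated. The unit is the patient-day: "for each patient and each day on oxygen prescription, the relative difference". The comparator is the "corresponding individual daily duration of oxygen prescription", labelled D_O2 prescribed. It is subtracted from the day's use in both differences and is also the denominator of the relative one.
- **Reporting.** "Both differences will be tabulated by study group, over the successive periods between the scheduled visits", and also globally. Period means are plotted, and each difference is analysed with the repeated-measures model already set out for average daily use (study group, period and their interaction). Tables, graphs and models are produced on all recordings and again without days on CPAP or NIV. They are then repeated in patients on LTOT (15 hours or more prescribed), over the period of their LTOT prescription.

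D_O2 prescribed has no other definition in the Protocol.

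**The concern.** A day's use should be judged against what was prescribed on that day. A whole-period average mixes earlier and later prescriptions, so after any change it matches neither. The daily difference then contains a component that has nothing to do with the patient's behaviour, and that component changes sign at the date of the change.

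The by-period profile of the compliance difference is the output meant to show how adherence to the prescription evolves. Prescription changes alone could create or hide a trend in it. They would also feed into the group-by-period interaction, where significance at the 0.10 level may prompt further separate analyses. Protocol 1.C singles out LTOT compliance for particular attention, so these outputs will be read.

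**Working it through.** The Protocol states no figure here, so there is none to reproduce. The check applies its rule to a patient whose recorded use equals the prescription in force every day. The true difference is then 0 on every day.

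**Inputs.** The formula is from 7.B.3.5. The prescribed hours and change dates are assumptions, over 365 days on oxygen; the 15-hour value is the Protocol's LTOT threshold.

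**Formulas.** With h1 hours for d1 days, then h2 hours for d2 days:

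- D = (h1 × d1 + h2 × d2) / (d1 + d2)
- Before the change: h1 − D, and 100 × (h1 − D) / D
- After the change: h2 − D, and 100 × (h2 − D) / D

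**Example in full.** For 15 then 18 hours, changed after day 182: D = (15 × 182 + 18 × 183) / 365 = 6024 / 365 = 16.504 h. Before: 15 − 16.504 = −1.50 h, or −9.1%. After: 18 − 16.504 = +1.50 h, or +9.1%.

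| Prescription (assumed) | Change after day | D (h) | Before | After |
|---|---|---|---|---|
| 15 to 18 h | 182 | 16.504 | −1.50 h (−9.1%) | +1.50 h (+9.1%) |
| 15 to 18 h | 91 | 17.252 | −2.25 h (−13.1%) | +0.75 h (+4.3%) |
| 8 to 16 h | 182 | 12.011 | −4.01 h (−33.4%) | +3.99 h (+33.2%) |
| 18 to 15 h | 182 | 16.496 | +1.50 h (+9.1%) | −1.50 h (−9.1%) |
| 16 to 8 h | 182 | 11.989 | +4.01 h (+33.5%) | −3.99 h (−33.3%) |

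Three results follow.

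1. **Direction.** An increase gives false under-use, then false over-use. A decrease gives the opposite.
2. **Cancellation.** Over all days the mean difference is [d1 × (h1 − D) + d2 × (h2 − D)] / (d1 + d2) = D − D = 0. The global mean is therefore free of the artefact when the recordings cover exactly the days used in D. If part of those days is left out, it need not be. That may happen in the LTOT-period repeat, in the repeat without CPAP or NIV days, or when the device is held for only part of the time.
3. **With the same-day prescription.** The difference is h1 − h1 = 0 before and h2 − h2 = 0 after, so it is zero in every period.

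**The case against.** The best defence is that the same-day prescription was meant. The compliance text works day by day and speaks of a corresponding duration. With a constant D, the day-level step would gain nothing, because the mean of (use − D)/D over days equals (mean use − D)/D. The averaging rule also stands under a different bold heading, next to a descriptive table of prescribed duration. This makes the same-day reading quite possible, but it is nowhere stated. The per-patient plots later in the same block use nearly the same phrase, including the word corresponding, for a patient-level value. A programmer who follows the only definition given would code the average.

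The limits on consequence stand in full. Section 7.B makes everything except the primary analysis exploratory and descriptive. Average daily use by period, and its model, do not involve D_O2 prescribed. Only oxygen users with a changed prescription are affected.

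A reader might infer three stronger things that the documents do not support.

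- **A biased comparison between arms.** Appendix 2 lists therapeutic adjustment among the possible decisions after an alarm, but nothing ties it to prescribed oxygen hours. Section 5.A.3 leaves oxygen prescription to centre practice and the investigator, without distinction by arm. The artefact can arise in both arms, and increases and decreases offset each other.
- **A particular shift in arm means.** This needs the share of patients who change and the size of the change, and the Protocol gives neither. If 10% to 30% changed, all in the same direction at mid-year, the shift would be about 0.9 to 2.7 points in each half-year for 15 to 18 hours, and about 3 to 10 points for 8 to 16 hours. The width of that range shows how little is known.
- **A fixed +33% in the LTOT repeat.** That value requires an average over all oxygen days, including those under 15 hours, to be carried into the LTOT-only period. If the average were recalculated over that period, it would vanish in the 8 to 16 hour example. The Protocol does not say which applies.

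**Conclusion.** The point holds as a defined term reused where a day-specific value is needed. Followed as written, the rule gives a fully compliant patient with a changed prescription non-zero differences by period. They are about 9% either way for a 15 to 18 hour change at mid-year and about 33% for 8 to 16 hours, with signs set by the direction of the change. These sizes rest on assumed prescriptions and change dates. The by-period tables, graphs and repeated-measures results for the two differences are exposed. Their global means are exposed only where the recordings do not cover all the days in the average. The number of patients concerned, and any imbalance between arms, cannot be known from the Protocol. The point is worth correcting because the text fixes a formula that misfires and the remedy is nearly free. It does not touch the primary conclusion.

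**What to change.** In the compliance paragraphs of 7.B.3.5, define D_O2 prescribed, in both the relative and the absolute difference, as the daily hours of the oxygen prescription in force on that calendar day. Then average the daily differences within each inter-visit period and globally. Keep the time-weighted mean for the descriptive table of prescribed duration and, if wanted, for the horizontal axis of the per-patient plots. Compute it over the same days as the NOWOX recordings it accompanies.

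The cost is one sentence and a merge by date in programming. Section 5.D already has the e-CRF record "start and, if applicable, end dates, daily prescribed hours of use" for oxygen therapy, so no new data are needed.
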